## **12 PROTOCOL VIOLATIONS**

A protocol violation occurs when the subject or investigator (Sponsor) fails to adhere to significant protocol requirements affecting the inclusion, exclusion, subject safety and primary endpoint criteria. Protocol violations for this study include, but are not limited to, the following:

- Failure to meet inclusion/exclusion criteria
- Failure by the study team to schedule every other week participant contact

Failure to comply with Good Clinical Practice (GCP) guidelines will also result in a protocol violation. The UCSF and UW IRBs will determine if a protocol violation will result in withdrawal of a subject.

When a protocol violation occurs, it will be discussed with the investigator and a Protocol Violation Form detailing the violation will be generated. This form will be signed by the investigator. A copy of the form will be filed in the site's regulatory binder and in the Sponsor's files.

## **13 DATA SAFETY MONITORING**

The Data Safety Monitoring Board (DSMB) will review data relating to safety and efficacy, to conduct and review interim analyses, and to ensure the continued scientific validity and merit of the study, according to the Data Safety Monitoring Board Operations Manual and a DMC Charter to be established for this protocol. There will be one interim review conducted by the DMC for the purpose of monitoring study conduct and assessing patient safety. Further details regarding the timing and content of the interim reviews is included in the statistical section below.

## **14 STATISTICAL METHODS AND CONSIDERATIONS**

Prior to the analysis of the final study data, a detailed Statistical Analysis Plan (SAP) will be written describing all analyses that will be performed. The SAP will contain any modifications to the analysis plan described below.

### **14.1 Data Sets Analyzed**

All patients who are randomized into the study will be included in the analysis.

### **14.2 Demographic and Baseline Characteristics**

The following demographic variables at screening will be summarized by study treatment group including (but not limited to): race/ethnicity, gender, age, dialysis vintage (number of years on maintenance dialysis), comorbidity.

### **14.3 Analysis of Primary Endpoint**

We will quantify the screen: enroll ratio. We will quantify rates of retention and adherence in each arm of the study and report characteristics of those lost to follow-up.

We will quantify % of patients in the home BP arm who can successfully complete home BP training, % who can transmit every other week home BP readings in a timely manner to the study team via any method and % who successfully implement electronic transfer of data via Bluetooth/smartphone.

Adverse events will be tabulated by treatment group and will include the number of patients for whom the event occurred, the rate of occurrence, and the severity and relationship to study intervention.

We will determine frequency of excessively high or low blood pressures, frequency of intra-dialytic hypotension and symptoms related to these in all enrollees.

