### 7.3 Measuring Home SBP

We will use the Microlife WatchBP Home A BT device.

After appropriate training by study personnel, study participants will be asked to take their own BP at home every two weeks.

- Home BP will be taken on a non-dialysis day
- Participants will be instructed to obtain a BP measure in the morning on a non-dialysis day (3 consecutive BP measures obtained at one sitting)
- Participants will be instructed to obtain a BP measure in the evening on a non-dialysis day (3 consecutive BP measures obtained at one sitting)

Participants will have several options to share the home blood pressure readings with the study team.

- For participants with a smart phone, the BP readings can be automatically downloaded via Bluetooth to an app then to a secure cloud server.
- Participants can download the readings from the home blood pressure device via USB drive and shared with the study team.
- Participants can keep a paper log of home blood pressure readings to share with the study team.
- Participants can text, phone or email the results to the study team.

We will allow assistance from family members or other caregivers and work in other ways with study participants to minimize burden of data transmission.

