#### **7.5 Treatment Adherence**

Participants in both treatment arms will have regular contact with the study coordinator (scheduled approximately every 2 weeks), where they will be reminded/encouraged to take all prescribed anti-hypertensive medications and medication reconciliation will be performed. For participants in the home BP treatment arm, home BP readings will be reviewed and assessed for adherence.

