## **9.2 Visit 1: Baseline Visit**

1. Update information obtained at screening visit
2. Record the following information from the dialysis records from the prior two weeks: estimated dry weight, pre-dialysis blood pressures, episodes of intra-dialytic hypotension
3. Randomize participant to one of two study arms
4. If participant is randomized to home BP arm, train participant on use and transmission of home BP measures
5. Schedule subject for next study contact in approximately 14 days, either during patient's regularly scheduled dialysis or a telephone call
6. Optional: Place 44-hour ambulatory blood pressure cuff and train patient on use (study team will also coordinate with patient return of 44-hour ambulatory blood pressure monitor.) Administer 44-Hour ABPM Experience Questionnaire.
7. Blood sample collected at beginning of dialysis treatment via dialysis access and usual dialysis procedures (at UW only)

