## **9.3 Visits 2-8 (occurring approximately every 2 weeks)**

1. Record any Adverse Experiences
2. Review any home BP measures (if applicable)
3. Concomitant medications review
4. Updated medical history/interim events/interim hospitalizations
5. BP medication review and assessment of adherence to BP medications

6. Review dialysis unit records: estimated dry weight, pre-dialysis blood pressures, episodes of intra-dialytic hypotension
7. Record any updated laboratory values (with corresponding date) taken from the dialysis records
8. Record vital signs, including weight and dialysis unit BP
9. Administer questionnaire of symptoms of hypotension during the last hemodialysis session: cramping (yes/no), dizziness/lightheadedness (yes/no), and fatigue (yes/no).
10. Ask open-ended question: "How long did it take you to recover from your last dialysis session" (responses in minutes or hours)
11. If subject is a woman of child-bearing age, she will also be asked about possible pregnancy (UW only).
12. Adjust estimated dry weight and medications as per study physician's recommendations

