## **10 ADVERSE EXPERIENCE REPORTING AND DOCUMENTATION**

### **10.1 Adverse Events**

An adverse event (AE) is any untoward medical occurrence during a clinical investigation and that does not necessarily have a causal relationship with the study intervention. An AE is therefore any unfavorable and unintended sign (including an abnormal laboratory finding), symptom or disease that may or may not be associated with the administration of a study intervention.

The study team will probe, via discussion with the subject and review of the medical record, for the occurrence of AEs during each subject visit and record the information in the site's source documents. Adverse events will be recorded in the patient CRF. Adverse events will be described by duration (start and stop dates and times), severity, outcome, treatment and relation to study intervention, or if unrelated, the cause.

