### **10.2.1 Serious Adverse Experience Reporting**

Study sites will document all SAEs that occur (whether or not related to study drug) per UCSF CHR and UW IRB Guidelines. The collection period for all SAEs will begin after informed consent is obtained and end after procedures for the final study visit have been completed.

In accordance with the standard operating procedures and policies of the local Institutional Review Board (IRB), the site investigator will report SAEs to the IRB.

We will collect data on potential adverse events from several sources and incorporate them into the adverse event database. These sources include:

- Reports from participants of any occurrences of concern to them, to be obtained from calls to toll-free or local study numbers provided in the Consent Form and included in all post-enrollment Contact Forms
- Laboratory database and reports of new hospitalizations

Adverse events data from the study-site specific call lines will be reviewed weekly, as will AE reports from all sources, by the site PI and site study clinician(s), any Serious Adverse Events that are identified will be reported promptly to the DSMB and IRB(s).

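### Only the home BP arm has home readings reviewed when adverse events are recorded, so events found through a home reading could add to that arm's AE count with no counterpart in the in-center arm

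*Combined protocol and SAP*

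**What the plan says.** Safety is one of the primary endpoints (Synopsis; Section 5.1). Section 14.3 sets out the reporting: "Adverse events will be tabulated by treatment group and will include the number of patients for whom the event occurred", together with rate, severity and relationship to the intervention. No test is specified.

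Section 10.1 gives the definition: "An AE is therefore any unfavorable and unintended sign (including an abnormal laboratory finding), symptom or disease". It also gives the method, which applies to both arms: "The study team will probe, via discussion with the subject and review of the medical record, for the occurrence of AEs during each subject visit". Section 10.2.1 lists further sources. They are participant reports ("Reports from participants of any occurrences of concern to them"), the laboratory database and new hospitalizations. Home BP readings are not on that list.

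Home monitoring belongs to one arm. Section 9.2: "If participant is randomized to home BP arm, train participant on use and transmission of home BP measures". Section 7.5: "For participants in the home BP treatment arm, home BP readings will be reviewed and assessed for adherence". In Section 9.3 the first task at Visits 2-8 is recording adverse experiences and the second is "Review any home BP measures (if applicable". Section 7.2 states that neither investigators nor participants are blinded.

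**The concern.** An AE table by arm is easiest to read when events had the same chance of being noticed in each arm. Here one arm has an extra window. A low or high value on the home monitor, or a symptom that a participant mentions because of that value, comes up at the contact where AEs are taken down. An asymptomatic out-of-range value would fit the Section 10.1 definition and the mild grade of the severity table. A participant in the in-center arm in the same state at home has no study monitor to show it.

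Any effect runs in one direction, since home readings can add events to the home arm and cannot add any to the other. It could also reach the relationship column, because Section 2.1 already names hypotension and dizziness as risks of the study medications, and Table 2 in Section 10.1 credits a known or expected response pattern. The rationale in Section 2 is that targeting dialysis-unit pressure may overtreat patients whose out-of-unit pressure is lower, so out-of-unit low pressure in the in-center arm is part of what the trial cares about. At stake is how the pilot's safety table is read, and possibly the single interim safety review in Section 13.

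**Working it through.** There is no plan figure to reproduce. The 50 participants are a budget choice (Section 14.5), with no event rate, effect or error rate attached.

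**1. What differs between arms, from the schedule**
- Home readings: "study participants will be asked to take their own BP at home every two weeks" (Section 7.3), with 3 measures in the morning and 3 in the evening, so 6 per reading day.
- Follow-up contacts: Visits 2 to 9, which is 8.
- Per participant: 8 × 6 = 48 planned readings.
- Home arm: 25 × 8 = 200 reading days, and 25 × 48 = 1,200 readings.
- In-center arm: 0.

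These are upper limits, because completion of home readings is itself an outcome (Section 5.1).

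**2. What does not differ**
- Contact about every 2 weeks (Section 7.5).
- AE probing by discussion and record review (Section 10.1).
- Symptom questions and review of intra-dialytic hypotension (Sections 5.1 and 8.2.3).
- Review of pre-dialysis pressures (Section 9.3). Taking 4 months as 16 weeks, that is about 3 × 16 = 48 pre-dialysis readings per participant in either arm.

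Only the home-reading component is one-sided.

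**3. Illustration of size**

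Let p be the probability that one home reading day leads to an AE entry. The documents do not give p; every value below is an assumption. With 8 independent reading days, the chance that a participant has at least one such entry is q = 1 − (1 − p)^8. Expected participants are 25q and expected events are 200p. If a share b of each arm has some other AE anyway (also assumed), the artificial difference in the proportion with any AE is (1 − b)q.

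| p | q | participants (25q) | events (200p) | difference, b = 30% | b = 50% | b = 70% |
|---|---|---|---|---|---|---|
| 0 | 0 | 0 | 0 | 0 | 0 | 0 |
| 0.5% | 3.9% | 1.0 | 1 | 2.8 points | 2.0 | 1.2 |
| 1% | 7.7% | 1.9 | 2 | 5.4 | 3.9 | 2.3 |
| 2% | 14.9% | 3.7 | 4 | 10.4 | 7.5 | 4.5 |
| 5% | 33.7% | 8.4 | 10 | 23.6 | 16.8 | 10.1 |

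If abnormal readings cluster in a few people, the event column stands but fewer participants are affected. Incomplete readings lower every column. The table shows how the count would respond to p; it does not estimate p.

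**The case against.** The strongest reply is that the mechanism rests on silence. No section makes a BP reading an AE. Section 10.1 mentions abnormal laboratory findings but not blood pressure, and Section 10.2.1 does not list home readings as a source. Section 7.5 reviews them for adherence, and Section 8.1 uses them to guide treatment. Extreme pressures have their own safety outcome in Section 5.1, whose example thresholds are dialysis-unit readings that both arms have. If staff keep to the listed sources, the effect is nil. This stands as a limit on the claim. It does not close the gap, because participant reports of anything that concerns them are an accepted source, nothing records that a monitor prompted the report, and the Section 5.1 thresholds are given only as examples.

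It also stands that the structured symptom questions ask about the last dialysis session, while home readings are taken on non-dialysis days; monitor-prompted symptoms would come in through general AE probing. Symptomatic events at home can be reported in either arm, and optional 44-hour ambulatory monitoring at Visits 1 and 9 is not restricted by arm. A reader might infer that the in-center arm's state at home goes wholly unseen, but the documents do not support that.

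Finally, the table is descriptive, and Section 14.5 says the pilot is not designed to find significant differences. The second safety objective concerns the home strategy itself, so events surfaced by home monitoring are arguably part of its profile. That is a reason to keep them in the full table. It does not make them comparable with an arm that had no monitor, and unequal detection distorts a descriptive count as it would a test.

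**Conclusion.** The concern holds in a limited form. Unequal opportunity for detection is built into the schedule: up to 1,200 home readings in one arm and none in the other, reviewed at unblinded contacts where AEs are recorded under a broad definition. Section 14.3 has nothing that would separate events found that way, so they could add to the home arm's count without a counterpart.

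A reader might infer that the home arm's count will be inflated, or that the arm measured more must show more events when true safety is equal. The documents do not support that, because they never say that a home reading is an AE. The size cannot be determined from them. It is zero if such readings are never recorded as AEs. Under assumed rates of 0.5% to 5% of reading days, with independent and fully completed days, about 1 to 8 of 25 participants would have such an entry, and fewer would be added to the any-AE count because some would already have another event. No sample-size or error-rate figure is affected. The point is worth acting on because the possible bias has one direction, falls on a primary safety table, and is hard to trace afterwards if the source was not recorded.

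**What to change.** Add a *how identified* field to the AE form: participant report, dialysis or medical record, hospitalization, laboratory, home BP reading only. Add a flag for participant reports prompted by a home reading; without it, a symptom mentioned because of a monitor value would be coded as an ordinary participant report and stay in the comparison.

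In Section 14.3, and in the detailed SAP that Section 14 says is still to be written:
- Keep the full AE table by arm.
- Add a by-arm line limited to sources available in both arms.
- List events identified only from, or prompted by, a home reading separately for the home arm.

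The field should be filled in when the event is recorded. The cost is one CRF field and one extra table line, and some home-arm events will appear in two places. The flag depends on staff asking what prompted a report, so it will reduce the asymmetry but may not remove it. No data are dropped and no treatment rule changes.

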### **14.4 Analysis of Secondary Endpoints**

In both groups, we will use descriptive statistics (such as mean and standard deviation) to quantify changes in pre-dialysis blood pressure and 44-hour ABMP results at the end of the study.

We will also describe patterns of dry weight target and blood pressure medication use (number and dosage).

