## PROTOCOL SYNOPSIS

TITLE	The BOLD Trial: B lood Pressure L owering in D ialysis Trial
PIs	[name], MSc [name], MAS
FUNDING ORGANIZATION	NIH-NIDDK and Satellite Healthcare
NUMBER OF SITES	2
RATIONALE	Treating home blood pressure may be better than treating dialysis unit blood pressure to improve outcomes in patients on maintenance hemodialysis
STUDY DESIGN	Randomized controlled trial
PRIMARY OBJECTIVE	
 
To determine the feasibility of and adherence to a strategy of dry weight adjustment and anti-hypertensive medication titration to achieve home systolic blood pressure <140 mmHg vs. a pre-dialysis systolic blood pressure <140 mmHg over 4 months.
 
To test the safety and tolerability of an intervention to achieve home systolic blood pressure <140 mmHg.
 

SECONDARY OBJECTIVES	
 
To determine acceptability of a Bluetooth-enable home blood pressure monitor in dialysis patients
 
To determine whether the strategy of targeting home systolic blood pressure versus in-center pre-dialysis systolic blood pressure leads to differences in blood pressure levels
 

NUMBER OF SUBJECTS	50 (or 25 in each of the two arms)
SUBJECT SELECTION CRITERIA	
Inclusion Criteria:
 
 
Provision of signed and dated informed consent form
 
Undergoing in-center, thrice weekly hemodialysis for treatment of end stage renal disease
 
Greater than 3 months since initiation of dialysis
 
Aged 18 years or above
 
Able to obtain a brachial blood pressure at dialysis and at home
 
 
Exclusion Criteria:
 
 
Pregnancy, anticipated pregnancy, or breastfeeding as this will require increase to more than three time a week dialysis and/or preclude use of some classes of blood pressure medications
 
Incarceration or institutionalized living which may prohibit measurement of home blood pressure
 
Participation in another intervention study that may affect blood
 

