	
pressure
 
4. Patients in whom systolic blood pressure is not measurable (e.g. those with left ventricular assist devices)
 
5. Hypotension: average pre-dialysis systolic blood pressure <100 mmHg over last 2 weeks prior to screening while not taking any blood pressure medications
 
6. Life expectancy <4 months
 
7. Anticipated living donor kidney transplant within 4 months

INTERVENTION	
 
• Dry weight and anti-hypertensive medication adjustment to target home systolic blood pressure vs. in-center pre-dialysis systolic blood pressure <140 mmHg
 

DURATION OF SUBJECT PARTICIPATION AND DURATION OF STUDY	The total duration of the study is expected to be 24 months
PRIMARY ENDPOINT	
 
• Feasibility of intervention
 
• Adherence to intervention
 
• Safety
 
• Tolerability
 

SECONDARY ENDPOINTS	
 
• Of the home BP participants, we will determine the modality they choose to transmit their home BP readings
 
• Differences in blood pressures between treatment groups as assessed by blood pressure at dialysis and 44-hour intra-dialytic ambulatory blood pressure
 

STATISTICS Primary Analysis Plan	
 
• We will quantify the screen: enroll ratio
 
• We will report the proportion of participants in the home BP arm that complete the training, percent of home BP readings completed over the study period, and mean time from home BP measurement to transmission to the study team.
 
• We will quantify rates of completion and drop out in each treatment arm.
 
• We will report rates of hypotension and hypertension in each treatment arm.
 
• We will quantify rate of intra-dialytic hypotension and symptoms related to intra-dialytic hypotension in each treatment arm.
 

Rationale for Number of Subjects	This pilot study is designed to test study logistics and optimize study interventions within the confines of a pilot study budget, not to find statistically significant differences between the two arms.

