### **4 STUDY DESIGN**

#### **4.1 Study Overview**

This is a two center, placebo-controlled, randomized 4 month trial of 50 subjects. This will be a pilot clinical trial to test the feasibility, adherence, safety and tolerability of a strategy of targeting home SBP <140 mmHg vs. dialysis-unit (pre-dialysis) SBP <140 mmHg. These targets will be achieved using an algorithm of estimated dry weight and anti-hypertensive medication adjustment. Home BP measures will be recorded every other week and transmitted to the study team. We have chosen the same SBP target and the same algorithm for both arms so we can test the effect of the *setting* of BP measurement (rather than a specific BP target or medication). Participants will have contact with the study team every 2 weeks to obtain information on interim study outcomes (updated medical history, completion of study questionnaires) and adjust estimated dry weight and anti-hypertensive medications. A final study visit will occur at 4 months.

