## 5.2 Secondary Outcomes

- Acceptability of a Bluetooth-enabled home BP monitor: of the home BP participants, we will determine the modality they choose to transmit their home BP readings (e.g. via Bluetooth, manual log, phone, etc)
- Differences in blood pressures between treatment groups as assessed by: (1) pre-dialysis SBP and DBP; (2) post-dialysis SBP and DBP and (3) 44-hour intra-dialytic ambulatory blood pressure monitoring from beginning to the end of the study (optional)

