## 7 STUDY TREATMENTS

### 7.1 Method of Assigning Subjects to Treatment Groups

Enrolled subjects, stratified by site, will be randomly assigned in a 1:1 allocation to one of 2 groups (25 patients at both sites): (1) home SBP<140 mmHg and (2) in-center pre-dialysis SBP<140 mmHg. Randomization will be in done via Redcap in random size blocks to minimize bias in randomization and to ensure balanced assignment at each site. Both groups will be followed in parallel.

Prior to conducting any study-related activities, written informed consent and the Health Insurance Portability and Accountability Act (HIPAA) authorization must be signed and dated by the subject or subject's legal representative. If appropriate, assent must also be obtained prior to conducting any study-related activities.

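### Section 14.4 plans only by-arm descriptive changes in blood pressure, although the secondary outcome is a between-group difference, and it leaves out post-dialysis BP

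*Combined protocol and SAP*

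**What the plan says.** The synopsis sets a secondary objective of learning whether targeting home systolic BP "versus in-center pre-dialysis systolic blood pressure leads to differences in blood pressure levels". Its secondary endpoint is "Differences in blood pressures between treatment groups as assessed by blood pressure at dialysis and 44-hour intra-dialytic ambulatory blood pressure". Section 5.2 is more specific: "Differences in blood pressures between treatment groups as assessed by: (1) pre-dialysis SBP and DBP; (2) post-dialysis SBP and DBP", followed by optional 44-hour ambulatory monitoring (ABPM).

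The analysis text for this outcome is section 14.4: for each arm, "we will use descriptive statistics (such as mean and standard deviation) to quantify changes in pre-dialysis blood pressure and 44-hour ABMP results", taken at study end. It also promises a description of dry weight targets and BP medication use.

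Four other places bear on the point:

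- Section 4.1 explains the design: "We have chosen the same SBP target and the same algorithm for both arms so we can test the effect of the" setting in which BP is measured.
- Section 7.1 gives the allocation: "Enrolled subjects, stratified by site, will be randomly assigned in a 1:1 allocation to one of 2 groups".
- Section 14 defers detail to an SAP to be written before the final analysis.
- Section 14.5 says the size of 50 was set by budget and that the pilot does not aim at statistically significant differences.

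**The concern.** The outcome is a comparison of arms, but the analysis describes each arm separately. A report could follow 14.4 to the letter and never state the quantity that 5.2 names, or how uncertain it is. Yet section 4.1 holds target and algorithm equal across arms so that the effect of measurement setting can be seen.

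There are three further gaps:

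- **Post-dialysis systolic and diastolic BP.** They are listed in 5.2 and absent from 14.4.
- **Baseline and site.** Baseline is collected and site is a stratum, but neither enters an analysis.
- **Definition of the dialysis-unit values.** The averaging rule and the end-of-study window are not given, so they could be chosen after the data are seen.

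**Working it through.** **Outcome against analysis**

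| BP measure in 5.2 | In 14.4? | Home minus in-center difference or CI planned? |
|---|---|---|
| Pre-dialysis SBP, DBP | Yes, change by group | No |
| Post-dialysis SBP, DBP | No | No |
| 44-hour ABPM (optional) | Yes, change by group | No |

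**Is post-dialysis BP collected?** At baseline (9.2) the instruction is "Record the following information from the dialysis records from the prior two weeks: estimated dry weight, pre-dialysis blood pressures, episodes of intra-dialytic hypotension". At Visits 2-8 (9.3) it is "Review dialysis unit records: estimated dry weight, pre-dialysis blood pressures, episodes of intra-dialytic hypotension", and Visit 9 repeats those procedures. Both name pre-dialysis BP only. Item 8 of 9.3 adds a general dialysis-unit BP, and Appendix 1 lists BP among the vital signs at every visit. However, section 1.1 uses the dialysis-unit term for pre-dialysis systolic BP. Collection is therefore unclear, not shown to be missing.

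**Timing.** ABPM is placed at Visits 1 and 9, and the baseline record window is two weeks. No section says how dialysis-unit readings are averaged or which readings form the end-of-study value.

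**Precision of the contrast.** The plan has no precision or power figure to reproduce. From the documents: n = 25 per arm (14.5). Assumed: equal SD at baseline and end of study of 20 mmHg (range 15 to 25), baseline-to-end correlation r from 0.3 to 0.7, no loss to follow-up, and site explaining no variance.

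Half-width of the 95% CI = t(0.975, df) × SD × √(2/n) × f, where

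- change score: f = √(2(1 − r)), df = 2n − 2 = 48, t = 2.011;
- end-of-study value alone: f = 1, df = 48;
- ANCOVA on arm, baseline and site: f = √(1 − r²), df = 2n − 4 = 46, t = 2.013.

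With SD 20, SD × √(2/25) = 5.657. At r = 0.5 the change score gives 2.011 × 5.657 × 1.000 = 11.4, and ANCOVA gives 2.013 × 5.657 × 0.866 = 9.9.

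| SD 20, 25 per arm | r = 0.3 | r = 0.5 | r = 0.7 | r = 0.9 |
|---|---|---|---|---|
| Change score (mmHg) | 13.5 | 11.4 | 8.8 | 5.1 |
| ANCOVA (mmHg) | 10.9 | 9.9 | 8.1 | 5.0 |
| End value alone (mmHg) | 11.4 | 11.4 | 11.4 | 11.4 |
| Change score minus ANCOVA (mmHg) | 2.6 | 1.5 | 0.7 | 0.1 |
| SE ratio, ANCOVA/change = √((1 + r)/2) | 0.806 | 0.866 | 0.922 | 0.975 |

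The change-score sample that matches ANCOVA with 25 per arm is 25 × 2/(1 + r), or 38.5, 33.3 and 29.4 per arm at r = 0.3, 0.5 and 0.7.

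| Other cases (r = 0.3, 0.5, 0.7) | Change score (mmHg) | ANCOVA (mmHg) |
|---|---|---|
| SD 15, 25 per arm | 10.1, 8.5, 6.6 | 8.1, 7.4, 6.1 |
| SD 25, 25 per arm | 16.8, 14.2, 11.0 | 13.6, 12.3, 10.2 |
| SD 20, assumed 15 per arm with ABPM | 17.7, 15.0, 11.6 | 14.3, 13.0, 10.7 |

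A simulation (SD 20, 25 per arm, 4,000 trials at each of r = 0.3, 0.5 and 0.7) gave mean half-widths within about 0.1 mmHg of these and coverage close to 95% for both methods.

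**The case against.** The strongest reply is that this is a 50-person, budget-sized pilot about feasibility, adherence, safety and tolerability. Describing a secondary outcome by arm is a legitimate choice there. The wording of 14.4 covers both groups and its list of statistics is open-ended, so a reader can subtract one mean change from the other. An SAP is promised. The precision figures rest on assumed inputs and compare two contrasts, neither of which is planned. The gain over change scores is small when r is high, and two-week averages would tend to raise r. No figure supports the site term.

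Much of this limits the size of the point but does not remove it. Section 14.5 rules out claims of significance, not an estimate with its interval. The unadjusted contrast can be rebuilt from arm means, SDs and numbers; the baseline- and site-adjusted one cannot. The promised SAP could close the gap, but none of the text available does so, and until then 14.4 is the plan.

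Three cautions stand. An end-of-study ANCOVA uses only participants with a final value, whereas 14.1 includes everyone randomised; the change summaries in 14.4 have the same problem. Under 8.1, dialysis-unit readings steer treatment in the in-center arm only, so a difference in pre-dialysis systolic BP needs careful reading. The optional ABPM group is self-selected.

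**Conclusion.** The concern holds, as a minor one. The mismatch between 5.2 and 14.4, and the absence of post-dialysis BP from 14.4, are plain on the text and need no assumption. Whether post-dialysis BP is being abstracted is an open question that the documents do not settle.

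The benefit of ANCOVA over change scores is illustrative. Under the assumptions above, its standard error is 19%, 13% and 8% smaller at r = 0.3, 0.5 and 0.7, and the gain almost vanishes at r = 0.9. Against end-of-study values alone it is 5%, 13% and 29% smaller. The intervals remain wide for a pilot of this size under either method, and no decision rule depends on this outcome.

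**What to change.** Put text such as the following in 14.4 or in the promised SAP:

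> For each BP outcome (pre-dialysis SBP and DBP, post-dialysis SBP and DBP, 44-hour ambulatory BP) we will report the home minus in-center difference with a 95% CI from ANCOVA of the end-of-study value on arm, baseline value and site. We will give the number contributing in each arm and make no significance claim. For dialysis-unit measures, baseline is the mean of the readings in the 2 weeks before Visit 1, and end of study is the mean of the readings in the 2 weeks before Visit 9.

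Keep the mean and SD by arm. Name post-dialysis SBP and DBP in the record reviews of 9.2, 9.3 and 9.4. Settle this first, because a later model cannot recover readings that were never abstracted.

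The cost is a few sentences, one simple model per outcome and, if post-dialysis BP is not already captured, slight extra abstraction in a review that already takes place. The price in reporting is CIs that are visibly wide, widest for the optional ABPM.
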